### 10.7 Interim analysis

No formal interim analysis is planned.

## 10.8 Sample size calculation

The sample size is calculated based on an estimate of median PFS with reasonable accuracy (width of 95% confidence interval) for first line treatment with everolimus in combination with anastrozole or letrozole. The progression-free survival (PFS) for the population of patients treated with anastrozole or letrozole alone as first line therapy is approximately 9 months (Mouridsen et al 2003, Bonneterre et al 2001). Combining everolimus, the median PFS is expected to increase to 11 – 14 months. Considering a recruitment period of 18 months (1.5 years) and one year of follow up after the last patient is enrolled the expected 95% CIs for median PFS for 200 patients with 10% lost to follow-up, are provided in the table below for median PFSs of 11, 12, 13 and 14 months.

Median PFS	Expected 95% CI	95% CI width
11 months	9.32, 12.98	3.66
12 months	10.13, 14.22	4.09
13 months	10.93, 15.46	4.53
14 months	11.73, 16.71	4.98

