## **2.2 Rationale for the study design**

This trial is designed to assess the progression free survival of patients treated with everolimus in combination with letrozole in the first line setting (primary study endpoint). It is also designed to evaluate the efficacy of continued therapy with everolimus in combination with a second endocrine agent, exemestane, in patients progressing on first line treatment (secondary study endpoint). Allowing patients to continue everolimus in combination with exemestane after progression will assess the effectiveness of continued treatment with everolimus in this patient population, who have progressed following first line treatment with everolimus plus letrozole. The study design will be open-label, single arm and will enroll a sufficient number of patients to allow a robust estimate of PFS in the first line setting.

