### **10.4.2 Statistical hypothesis, model, and method of analysis**

The primary efficacy endpoint, PFS, will be analyzed based on the data from FAS. The median PFS as well as the 25th and 75 quartile will be estimated using the Kaplan-Meier method and presented along with 95% confidence intervals.

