### **10.4.3 Handling of missing values/censoring/discontinuations**

In this study the primary analysis of PFS for first line treatment will be performed 12 months after the last patient's recruitment. The analysis of PFS for second line treatment will be performed 6 months later (18 months after the last patient's recruitment) provided that the number of patients in second line treatment is adequate for a reliable PFS analysis. Otherwise, this analysis will be performed 24 months after the last patient's recruitment. For the analyses, PFS will be censored on the date of last adequate tumor assessment, if no PFS event is observed before the cut-off date or before the date a new anti-neoplastic therapy or another investigational treatment for cancer is started, whichever occurs earlier. If a PFS event is observed after two or more missing or non-adequate tumor assessments, then the date of progression will be censored at the latest occurring evaluable tumor assessment. If a PFS event is observed after a single missing or non-evaluable tumor assessment, the actual date of event will be used.

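### The 95% CI widths that justify 200 patients are those of an exponential-model median; the planned Kaplan-Meier interval is expected to be about 15–24% wider

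*Protocol*

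**What the plan says.** Section 10.8 sizes the trial on precision alone, in terms of "reasonable accuracy (width of 95% confidence interval") for the median. There is no hypothesis, null value or power. The planning inputs are given as "Considering a recruitment period of 18 months (1.5 years) and one year of follow up after the last patient is enrolled", and the effect assumption is that "Combining everolimus, the median PFS is expected to increase to 11 – 14 months", against approximately 9 months for anastrozole or letrozole alone. The section then states that "the expected 95% CIs for median PFS for 200 patients with 10% lost to follow-up, are provided in the table below":

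| Median PFS (months) | Expected 95% CI | Width |
|---|---|---|
| 11 | 9.32, 12.98 | 3.66 |
| 12 | 10.13, 14.22 | 4.09 |
| 13 | 10.93, 15.46 | 4.53 |
| 14 | 11.73, 16.71 | 4.98 |

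Section 10.4.2 fixes the primary analysis: the median and quartiles of PFS "will be estimated using the Kaplan-Meier method and presented along with 95% confidence intervals". Section 10.4.3 puts that analysis 12 months after the last patient's recruitment, which agrees with the follow-up assumed in 10.8. Section 2.2 relies on the sizing when it says that the study "will enroll a sufficient number of patients to allow a robust estimate of PFS in the first line setting".

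**The concern.** The precision of an estimated median depends on the estimator. An exponential model uses every event, early or late, to estimate one hazard, and the standard error of the log median is 1/√events. A Kaplan-Meier median assumes no shape, so its precision depends on the variance of the survival curve at 0.5 and on how steep the curve is there. Even if nobody were censored before the median, its log-scale standard error under an exponential truth would be 1/(ln 2 × √n), which is larger than 1/√events for this design.

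If the table holds for the first estimator and the trial reports the second, section 10.8 promises a precision that its own primary analysis does not deliver. Interval width is the only quantitative support for 200 patients. A reader will also set the lower limits beside the 9-month figure in the same section: as printed, all four exceed 9.

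**Working it through.** **Inputs.** From section 10.8: N = 200, 18 months' recruitment, 12 months' further follow-up, 10% lost, medians m = 11 to 14. The protocol does not state the following, which are assumed here: uniform accrual, exponential PFS, and exponential loss reaching 10% at 30 months.

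**Step 1: reproduce the printed table.**

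- Event hazard λ = ln 2/m; loss hazard η = −ln(0.9)/30 = 0.00351; total h = λ + η.
- With administrative censoring uniform between 12 and 30 months, expected events are d = 200 × (λ/h) × [1 − (e^(−12h) − e^(−30h))/(18h)].
- Interval: m × exp(±1.96/√d).

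For m = 11: λ = 0.06301, h = 0.06653, event probability 0.6987, d = 139.7. Then 1.96/√139.7 = 0.1658 and exp(0.1658) = 1.180, so the limits are 11/1.180 = 9.32 and 11 × 1.180 = 12.98.

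| m | d | Computed CI | Printed CI |
|---|---|---|---|
| 11 | 139.7 | 9.32–12.98 | 9.32–12.98 |
| 12 | 133.8 | 10.13–14.22 | 10.13–14.22 |
| 13 | 128.2 | 10.93–15.46 | 10.93–15.46 |
| 14 | 123.1 | 11.73–16.71 | 11.73–16.71 |

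All eight limits agree to two decimals. Other readings of the 10% loss give widths of 3.61 to 3.81 at m = 11, close to the printed 3.66 but not equal to it. The table is therefore, with little doubt, the interval from a fitted exponential model.

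**Step 2: the same inputs with the planned estimator.**

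- Greenwood variance at the median: Var[S(m)]/S(m)² = I/200, where I is the integral from 0 to m of λ/[e^(−λt) e^(−ηt) G(t)] dt. G(t) = 1 up to 12 months and (30 − t)/18 after that.
- Delta method to the log median: SE = √(I/200)/ln 2, because the density at the median is S(m) × λ and λm = ln 2.
- Interval: m × exp(±1.96 × SE).

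For m = 11: I = 1.022, √(1.022/200) = 0.0715, SE = 0.0715/0.6931 = 0.1031, and the interval is 8.99–13.46. For comparison, the exponential SE is 1/√139.7 = 0.0846, and the simple bound 1/(ln 2 × √200) is 0.1020.

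| m | Kaplan-Meier CI | Width | Printed width | Excess |
|---|---|---|---|---|
| 11 | 8.99–13.46 | 4.48 | 3.66 | 22% |
| 12 | 9.80–14.69 | 4.89 | 4.09 | 20% |
| 13 | 10.61–15.92 | 5.31 | 4.53 | 17% |
| 14 | 11.42–17.17 | 5.75 | 4.98 | 15% |

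**Step 3: finite-sample check.** Mean widths of simulated Kaplan-Meier intervals (10,000 trials per scenario, same accrual and loss), for medians 11, 12, 13 and 14:

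- log-log limits: 4.49, 4.92, 5.42, 5.90;
- linear limits: 4.46, 4.88, 5.38, 5.87;
- log limits: 4.58, 5.02, 5.54, 6.07.

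A separate simulation of 4,000 trials per scenario with log-log limits gave 4.53, 4.98, 5.41 and 5.91, an excess of 24%, 22%, 19% and 19%.

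**Step 4: sensitivity to the loss assumption.** The asymptotic excess over the printed widths is 18–25% under other readings of 10% loss with 200 enrolled, 20–28% with 180 evaluable patients, and 14–21% with no loss at all.

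**Step 5: the lower limit at a median of 11.** ln(11/9) = 0.2007. The chance that the lower limit exceeds 9 is Φ(0.2007/SE − 1.96). With SE = 0.0846 this is Φ(0.41), about 66%; with SE = 0.1031 it is Φ(−0.01), about 49%. In simulations with log-log limits it was about 44–45%.

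**The case against.** The table contains no arithmetic slip: every limit is right for an exponential median, and section 10.8 names no method that it then breaks. The exponential form, uniform accrual and loss pattern are inferred from the match, and the Kaplan-Meier figures also assume an exponential truth. Section 10.8 sets no maximum width, so nothing stated fails at 4.5 months instead of 3.7. Nine months is background, not a success criterion; the asymptotic lower limit at a median of 11 is 8.99, a hair below it, and in the other three scenarios the lower limit stays well above 9. The final report will show the actual Kaplan-Meier interval whatever the planning table said. Amendment 5 records that enrolment closed at 202 patients, with the last first visit on 17-Dec-2014, so the size can no longer change.

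Most of this stands, and it limits the consequence: type I error, power, the estimate and patient care are untouched, and the 9-month comparison is a matter of how the table reads. It does not rescue the table. Section 10.8 presents these as the expected intervals for this trial's median PFS, and the only median PFS analysis planned is Kaplan-Meier. The agreement of eight limits to two decimals makes the inference about method strong, and the excess persists under every reading of the loss.

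**Conclusion.** The concern holds. The printed widths belong to an estimator the protocol does not plan to use. Under the planned Kaplan-Meier analysis the expected 95% interval is about 15–22% wider asymptotically. In simulation it is about 18–25% wider, depending on the transformation used for the limits. Taken the other way, the printed widths are about 13–20% too narrow. For Kaplan-Meier intervals to reach the printed widths, about 298, 285, 274 and 266 patients would be needed at medians of 11, 12, 13 and 14 months.

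The result rests on exponential PFS, uniform accrual over 18 months, and 10% exponential loss over 30 months, the combination that reproduces the table. The choice among linear, log and log-log limits moves the figures by a few percentage points and does not change the conclusion. Because precision is the sole justification for N, the stated precision should be that of the primary analysis.

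**What to change.** In section 10.8, replace the table with the intervals expected from the Kaplan-Meier analysis and say that they are non-parametric limits: about 9.0–13.5, 9.8–14.7, 10.6–15.9 and 11.4–17.2 months, with widths of about 4.5, 4.9, 5.3–5.4 and 5.8–5.9. State the distribution, accrual pattern, loss model and interval method behind them.

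Alternatively, keep the present table, label it as exponential-model precision, print the Kaplan-Meier widths beside it, and add the exponential-model interval as a secondary estimate in the analysis section.

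Either is a text change. Its only cost is that the stated precision becomes less favourable; it does not call for more patients or alter the primary analysis.

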## 11 Ethical considerations and administrative procedures

### 11.1 Regulatory and ethical compliance

This clinical study was designed, shall be implemented and reported in accordance with the ICH Harmonized Tripartite Guidelines for Good Clinical Practice, with applicable local regulations (including European Directive 2001/20/EC and US Code of Federal Regulations Title 21), and with the ethical principles laid down in the Declaration of Helsinki.

### 11.2 Responsibilities of the investigator and IRB/IEC/REB

The protocol and the proposed informed consent form must be reviewed and approved by a properly constituted Institutional Review Board/Independent Ethics Committee/Research Ethics Board (IRB/IEC/REB) before study start. Prior to study start, the investigator is required to sign a protocol signature page confirming his/her agreement to conduct the study in accordance with these documents and all of the instructions and procedures found in this protocol and to give access to all relevant data and records to Novartis monitors, auditors, Novartis Clinical Quality Assurance representatives, designated agents of Novartis, IRBs/IECs/REBs and regulatory authorities as required.

### 11.3 Informed consent procedures

Eligible patients may only be included in the study after providing written (witnessed, where required by law or regulation), IRB/IEC/REB-approved informed consent.

Informed consent must be obtained before conducting any study-specific procedures (i.e. all of the procedures described in the protocol). The process of obtaining informed consent should be documented in the patient source documents. The date when a subject's original Informed Consent for the Core Phase was actually obtained will be captured in their CRFs; the date for any subsequent reconsent will be stored in the source document

Novartis will provide to investigators, in a separate document, a proposed informed consent form (ICF) that is considered appropriate for this study and complies with the ICH GCP guideline and regulatory requirements. Any changes to this ICF suggested by the investigator must be agreed to by Novartis before submission to the IRB/IEC/REB, and a copy of the approved version must be provided to the Novartis monitor after IRB/IEC/REB approval.

#### **11.4 Discontinuation of the study**

Novartis reserves the right to discontinue this study under the conditions specified in the clinical study agreement. Specific conditions for terminating the study are outlined in [Section 4.2](#).

#### **11.5 Publication of study protocol and results**

Novartis assures that the key design elements of this protocol will be posted in a publicly accessible database such as clinicaltrials.gov. In addition, upon study completion and finalization of the study report the results of this study will be either submitted for publication and/or posted in a publicly accessible database of clinical study results.

#### **11.6 Study documentation, record keeping and retention of documents**

Each participating site will maintain appropriate medical and research records for this trial, in compliance with Section 4.9 of the ICH E6 GCP, and regulatory and institutional requirements for the protection of confidentiality of subjects. As part of participating in a Novartis-sponsored study, each site will permit authorized representatives of the sponsor(s) and regulatory agencies to examine (and when required by applicable law, to copy) clinical records for the purposes of quality assurance reviews, audits and evaluation of the study safety and progress.

Source data are all information, original records of clinical findings, observations, or other activities in a clinical trial necessary for the reconstruction and evaluation of the trial. Examples of these original documents and data records include, but are not limited to, hospital records, clinical and office charts, laboratory notes, memoranda, subjects' diaries or evaluation checklists, pharmacy dispensing records, recorded data from automated instruments, copies or transcriptions certified after verification as being accurate and complete, microfiches, photographic negatives, microfilm or magnetic media, x-rays, and subject files and records kept at the pharmacy, at the laboratories, and medico-technical departments involved in the clinical trial.

Data collection is the responsibility of the clinical trial staff at the site under the supervision of the site Principal Investigator. The study case report form (CRF) is the primary data collection instrument for the study. The investigator should ensure the accuracy, completeness, legibility, and timeliness of the data reported in the CRFs and all other required reports. Data reported on the CRF, that are derived from source documents, should be consistent with the source documents or the discrepancies should be explained. All data requested on the CRF must be recorded. Any missing data must be explained. Any change or correction to a paper CRF should be dated, initialed, and explained (if necessary) and should not obscure the original

entry. For electronic CRFs an audit trail will be maintained by the system. The investigator should retain records of the changes and corrections to paper CRFs.

The investigator/institution should maintain the trial documents as specified in Essential Documents for the Conduct of a Clinical Trial (ICH E6 Section 8) and as required by applicable regulations and/or guidelines. The investigator/institution should take measures to prevent accidental or premature destruction of these documents.

Essential documents (written and electronic) should be retained for a period of not less than fifteen (15) years from the completion of the Clinical Trial unless Sponsor provides written permission to dispose of them or, requires their retention for an additional period of time because of applicable laws, regulations and/or guidelines

### **11.7 Confidentiality of study documents and patient records**

The investigator must ensure anonymity of the patients; patients must not be identified by names in any documents submitted to Novartis. Signed informed consent forms and patient enrollment log must be kept strictly confidential to enable patient identification at the site.

### **11.8 Audits and inspections**

Source data/documents must be available to inspections by Novartis or designee or Health Authorities.

### **11.9 Financial disclosures**

Financial disclosures should be provided by study personnel who are directly involved in the treatment or evaluation of patients at the site - prior to study start.

## **12 Protocol adherence**

Investigators ascertain they will apply due diligence to avoid protocol deviations. Under no circumstances should the investigator contact Novartis or its agents, if any, monitoring the study to request approval of a protocol deviation, as no authorized deviations are permitted. If the investigator feels a protocol deviation would improve the conduct of the study this must be considered a protocol amendment, and unless such an amendment is agreed upon by Novartis and approved by the IRB/IEC/REB it cannot be implemented. All significant protocol deviations will be recorded and reported in the CSR.

### **12.1 Amendments to the protocol**

Any change or addition to the protocol can only be made in a written protocol amendment that must be approved by Novartis, Health Authorities where required, and the IRB/IEC/REB. Only amendments that are required for patient safety may be implemented prior to IRB/IEC/REB approval. Notwithstanding the need for approval of formal protocol amendments, the investigator is expected to take any immediate action required for the safety of any patient included in this study, even if this action represents a deviation from the protocol. In such cases, Novartis should be notified of this action and the IRB/IEC at the study

site should be informed according to local regulations (e.g. UK requires the notification of urgent safety measures within 3 days) but not later than 10 working days.

## 14 Appendices

### 14.1 Appendix 1: Oral Stomatitis Daily Questionnaire (OSDQ)

#### Oral Stomatitis Daily Questionnaire

The following questions ask about the effect of your mouth and throat soreness on your ability to perform regular daily activities. By mouth and throat soreness we mean any inflammation of the mouth and throat, with redness, irritation, and/or swelling or mouth ulcers. Think about the current episode of mouth and throat soreness only. This questionnaire includes 6 questions. Please reserve some time (5 minutes) for answering the questions. Answer every question by selecting the answer as indicated. If you are unsure about how to answer a question, please give the best answer you can. Try to respond to questionnaire each day at same of the day.

**Table 14-1 Oral Stomatitis Daily Questionnaire**

1. What is the date today?	DD – MM – YYYY																
1b. When did you experience the first symptoms of mouth and throat soreness? (only ask this question on Day 1 of the questionnaire)	DD – MM – YYYY																
2. How would you rate your OVERALL HEALTH during the PAST 24 HOURS?																	
Worst possible	Half-way between	Perfect health	worst possible and perfect health														
0 1 2 3 4 5 6 7 8 9 10																	
CIRCLE A NUMBER																	
3. During the PAST 24 HOURS, how much MOUTH AND THROAT SORENESS did you have?																	

 
 No soreness	.....	0	
 
 A little soreness	.....	1	
 
 Moderate soreness	.....	2	
 
 Quite a lot of soreness	.....	3	
 
 Extreme soreness	.....	4	
 
		No soreness	.....	0	A little soreness	.....	1	Moderate soreness	.....	2	Quite a lot of soreness	.....	3	Extreme soreness	.....	4	 
 If you circled 0, please skip to Question 5 

No soreness	.....	0															
A little soreness	.....	1															
Moderate soreness	.....	2															
Quite a lot of soreness	.....	3															
Extreme soreness	.....	4															
CIRCLE A NUMBER																	
4. During the PAST 24 HOURS, how much did MOUTH AND THROAT SORENESS limit you in each of the following activities?																	
		Not Limited	Limited A Little	Limited Some	Limited A Lot	Unable To Do											
a. Swallowing		.....0	1	2	3	4											
b. Drinking		.....0	1	2	3	4											
c. Eating		.....0	1	2	3	4											
d. Talking		.....0	1	2	3	4											
e. Sleeping		.....0	1	2	3	4											
		CIRCLE A NUMBER for each question															

---

1. What is the date today? DD – MM – YYYY

---

5. During the PAST 24 HOURS, how severe was the PAIN in your MOUTH?

---

No pain at all      Unbearable pain

---

0 1 2 3 4 5 6 7 8 9 10  
CIRCLE A NUMBER

---

6. During the PAST 24 HOURS, how much did your MOUTH AND THROAT SORENESS affect your ability to do your regular daily activities?

By regular activities, we mean the usual activities you do, such as employment (working for pay), work around the house, shopping, childcare, exercising, studying, etc. Think about times you were limited in the amount or kind of activities you could do and times you accomplished less than you would like. If MOUTH AND THROAT SORENESS affected your activities only a little, choose a low number.

Choose a high number if MOUTH AND THROAT SORENESS affected your activities a great deal.

---

Consider only how much during the PAST 24 HOURS, MOUTH AND THROAT SORENESS affected your ability to do your regular daily activities.

Had no effect on my daily activities Completely prevented me from doing my daily activities

---

0 1 2 3 4 5 6 7 8 9 10  
CIRCLE A NUMBER

[figure not shown]
---

**14.2 Appendix 2: Guidelines for response, duration of overall response, TTF, TTP, progression-free survival and overall survival (based on RECIST version 1.0)**

## Glossary

---

CR	Complete response
CRF	Case Report Form
CSR	Clinical Study Report
CT	Computed tomography
DFS	Disease-free survival
eCRF	Electronic Case Report Form
FPFV	First patient first visit
MRI	Magnetic resonance imaging
LPLV	Last patient last visit
OS	Overall survival
PD	Progressive disease
PFS	Progression-free survival
PR	Partial response
RAP	Report Analysis Preparation
RECIST	Response Evaluation Criteria in Solid Tumors
SD	Stable disease
TTF	Time to treatment failure
TPP	Time to progression
UNK	Unknown

---

